Product will be packaged for each in-person cohort study visit as follows: (1) Baseline to Week 4: During the first week after baseline, when participants start and ramp up their dose, standard multi-compartment pill organizer containers will be provided to study participants with their assigned dosing regimen (as indicated above). In addition, participants will be provided 28 days of their maintenance twice daily dose in a standard child resistant-pill bottle. This will allow for an extra 7 days of IP to account for delays in attending the Week 4 visit. (2) Week 4 and Week 8: Medication will be provided in a pill

bottle at each visit, and in order to assure adequate supply in case of a delay in study visits, each container will contain enough product to last 5 weeks. All containers will be child-resistant for added protection, and labeled appropriately for the study.

Product will be packaged **for the remote cohort** as follows: product will be mailed after the second baseline visit. The first week of starting the medication, when participants start and ramp up their dose, standard 7-day multi-compartment pill organizer containers will be provided to study participants with their assigned dosing regimen (as indicated above). In addition, participants will be provided 12 weeks of their maintenance twice daily dose in a standard child resistant-pill bottle. All containers will be child-resistant for added protection, and labeled appropriately for the study.

Product Education Information. When participants are provided Investigational Product the first time (Screening/Baseline 1 or 2), they will be given a consumer-friendly handout, Chantix Use and Safety Information (Appendix 12) that includes information on how to use the medication, smoking cessation withdrawal symptoms, side effects and adverse events, and information on smoking cessation quitlines. This handout is a modification of the FDA-approved Chantix Medication Guide (Appendix 14), which was modified to meet needs of the study. The handout will include information on setting a quit date that exists on the Chantix™ website. The recommendation will be to set a quit date for Day 8 of medication use, or up to 30 days after starting the study product. Note that participants in all study conditions will have product available for a maximum of 12 weeks. If participants wish to use the medication beyond 12 weeks, they will need to contact their own health care provider for a prescription that they can fill at their own expense. We will assess at each follow-up visit whether any participants used varenicline beyond the 12 weeks of this study.

Blinding. Our statistician will create the code that will allow identification of which numbered product is varenicline or placebo, and the code will be maintained in a sealed envelope in a locked cabinet by the ASU and LACT study sites that can be readily accessed in case of emergencies.

Medication Cost. There will be no medication cost to participants. Because some of the participants will receive placebo, charging for the product would not be reasonable. In addition, this design is consistent with the approach approved by the FDA when testing NRT OTC studies, so we want to use a design that has potential relevance to the FDA.

Adverse Events

Handling Adverse Events. Multiple very large studies have demonstrated that varenicline has a safety profile that is very similar to NRT⁵. Clinical trials to date indicate that varenicline utilization results in very few serious adverse events. However, we will take tracking and management of adverse events very seriously (as we have in our previous studies). As indicated above, we will make sure to assess adverse events that might reflect exacerbation of any reported or unreported psychiatric disorders.

Adverse Event (AE) Definitions. Any negative event subsequent to signing consent but prior to the week 13 visit will be considered a potential adverse event to be addressed and followed, regardless of whether it is related to use of study medication. Examples of AEs include: (1) Clinical signs and symptoms, (2) Abnormal test results, (3) Worsening of existing medical conditions. The licensed medical professional (LMP) will consider adverse events serious if the event: (1) is life threatening, (2) results in death, (3) leads to incapacity, hospitalization, or serious impairment of normal life, (4) congenital abnormality or birth defect. Serious AEs will be reported to the IRB within 24 hours of the site becoming aware of the event. Once an adverse or serious adverse event is identified, it must be followed and recorded, such that subsequent to the designation each event

outcome should be characterized as follows: 1 = Still present, 2 = Resolved with Sequelae, 3 = Resolved without Sequelae, 4 = Lost to follow-up/Unknown, 5 = Death.

Determination of Severity. The study coordinators will make a determination of AE severity and provide a grade for each event according to the following criterion: Mild: Symptoms cause little discomfort, are easily tolerated, and do not significantly interfere with normal everyday activities. Moderate: Symptoms are uncomfortable and interfere with normal everyday activities. Severe: Symptoms cause significant impairment of everyday activities, incapacitation, or death

Determination of Causality. The LMP will make a determination the causality of each adverse event in relation to the study medication using the following criteria: 1 = Definite, 2 = Probable, 3 = Possible, 4 = Remote, 5 = Definitely Not

Process for Handling AEs. At each visit and post-cessation call (and via EMA, see sub-study below), every participant will be asked to report on health status and adverse events. In addition, study participants will be instructed verbally and in writing to contact the study staff immediately if any health problem causes disruption in the participant's life — though participants will be informed to call 911 if they are experiencing any potentially life-threatening problems. Calls to the study staff will be triaged to determine if the study LMP should be contacted. The Arizona State University and LACT study physicians will address any medical problems that might arise (including working with each participant's health care provider if needed).

AE Reporting Period. All events not resolved or unrecovered by week 13 will be followed for 30 days after that date to assess status. Any participants lost to follow-up after a reported AE or serious AE will have 'unknown' indicated for that event.

Participant Payment

Main Study and Sub-studies. Note that all study participants will receive compensation for time and/or travel to the study sites as well as completing telephone visits during the treatment and follow-up study phases. Participants in the in-person cohort will be paid \$50 compensation for the screening/baseline visit, \$25 compensation for completing each of the weeks 2 and 13 telephone visits, \$50 for completing the in-clinic visits at weeks 4 and 8, and \$100 for completing the in-clinic week 12 visit (total of \$250), regardless of their smoking status. In addition, study participants will be compensated \$50 to come into the study sites to complete electronic questionnaires and to provide a breath CO if they report 7-day point prevalence abstinence at the 6-month follow-up call. Given the attrition that occurs in many smoking cessation studies, especially those that assess OTC medications, compensation for key study visits is essential.

Participants in the Remote Cohort will be paid \$50 combined for screening/baseline visits 1 and 2, \$25 compensation for completing each of the weeks 2 and 13 visits, \$50 for the visits at weeks 4 and 8, and \$100 for completing the week 12 visit (total for \$200), regardless of their smoking status. In addition, remote study participants will be compensated \$50 electronic questionnaires and to provide a urine sample for cotinine analysis if they report 7-day point prevalence abstinence at the 6-month follow-up call. Compensation will be paid to participants electronically.

Participants in the sub-studies will also be compensated. (1) EMA sub-study: Participants (total N = 75, or 25/medication condition) in the EMA sub-study will receive an additional \$30 for completion of Week 1 EMA assessments and \$40 for Week 2 EMA assessments. To encourage compliance with the EMA protocol and decrease incidence of missing data, sub-study participants will receive an additional \$10 in Weeks 1 and 2 if they complete 6 of 7 daily diaries, and will receive an additional \$10 in Weeks 1 and 2 if they respond to at least 3 scheduled prompts a day in each week. In total, EMA participants will

be compensated an additional \$70 to \$110 at the Week 4 visit, depending on protocol compliance.

EMA Sub-Study

Methods. We will randomly assign 25 people from each condition to participate in the EMA sub-study that lasts two weeks after the participants begin using varenicline, and they will be informed in the consent form at the Baseline/Screening visit that they may be asked to participate in the sub-study. We will use two types of EMA data assessments: (1) evening daily diaries to collect information on concrete behaviors (e.g., smoking and taking medication) that occurred that day, and (2) scheduled prompts to assess states (e.g. mood, craving, nausea) that fluctuate throughout the day (Appendix 13). Data will be collected using scheduled text messages linked to Qualtrics, which provides HIPPA-compliant data collection. At the Baseline/Screening visit, the research assistant will enroll substudy participants in the text message EMA data collection and will train participants how to respond to the scheduled prompts and the daily diary EMA surveys. The evening daily diary will include two brief questions on cigarette and varenicline pill consumption that day. In addition to the daily diary, participants will also respond to up to five scheduled prompts throughout the day. The first scheduled prompt will occur at 9am, and will include five brief questions on vivid dreaming and sleep quality from the last night, momentary nausea, momentary mood, and momentary craving. After the first scheduled prompt of the day is completed, subsequent scheduled prompts will ask about momentary nausea, mood, and craving only. Participants will be prompted to complete scheduled surveys at waking and at every four hours. Scheduled prompts will expire 30 minutes after their scheduled time; evening daily diaries can be completed any time after their scheduled time until midnight.

EMA Data Collection Summary. Table 3 shows the information and frequency that will be collected via EMA.

Table 3. EMA schedule of assessments.

	Baseline	Week	
		1	2
Assignment to EMA sub study	Χ		
Subject review of Varenicline Label	X		
Text message instructions	X		
Scheduled prompts			
Vivid dreaming (last night)		X	Х
Sleep quality (last night)		X	Х
Nausea (current)		X	Х
Mood (current)		X	Х
Cigarette craving (current)		X	Х
Daily diaries			
Number of cigarettes smoked that		Х	Х
day		^	
Varenicline taken that day		X	X
Additional thoughts/feelings?		X	Χ

EMA compliance and feasibility. The EMA scheduled prompts and daily diary are extremely brief. Similar assessments from [name] Study took typical

participants no more than 90 seconds to complete. To reduce missing data, participants who miss more than two sequential days of evening daily diaries or complete fewer than three scheduled prompts a day for two sequential days will receive encouragement texts and calls from an RA to troubleshoot any problems with the app and encourage compliance.

Definitions of Success

FDA Abstinence Criteria. As indicated earlier, in all studies that assess medications for smoking cessation, the FDA typically requires verification of 28 days of continuous abstinence, i.e.; not a single puff from a single cigarette. The FDA does not require the 'clock' to start at a consistent time point after study enrollment. Thus, in many studies the 'clock' on that 28 days begins two weeks after study medication has begun, while in other studies the 'clock' starts at a different time point. In the current study, we will follow the protocol used in the varenicline pivotal trials. ^{6,17-20} The primary study outcome in the proposed study will be continuous abstinence between weeks 8 and 12 after study medication has begun. Subjects who are randomized but who never obtain medication will be considered treatment failures and will be included in the denominator in the intent-to-treat analyses.

D. DATA SAFETY MONITORING PLAN

Participant Safety. This study includes the use of a medication, varenicline, that is FDA-approved, as well as the same medication at a lower dose than approved by the FDA, in order to assess whether smokers can choose and use the medication without a healthcare provider prescription. Given the existing data, the likelihood of participants experiencing a serious adverse event from the use of varenicline is very low. In fact, in one of the largest smoking cessation studies ever conducted, the adverse events related to varenicline were similar to those from the nicotine patch, which is already approved as an OTC medication.

However, we will monitor very carefully the screening and ongoing participation of all participants. Study participants will only be allowed to participate and receive medication if the study licensed healthcare provider at each site has approved their participation after reviewing screening documents. Regular visits as well as assessments between visits will provide updates on potential adverse events, and any serious events will be assessed (including for causality) by the study physicians and reported to Western IRB and the study sponsor (National Institute on Drug Abuse/NIH) within 24 hours.

We will also identify an independent safety-monitoring panel (comprised of an MD and two additional scientists to be determined) who receive reports once a year on participant safety, protocol violations, medication use, and any other relevant topics in order to assure patient safety and study integrity. The safety-monitoring panel will assess all adverse events, and will make an independent recommendation on how study staff should address any concerns that they have raised. Their report will be maintained in the study file notebook.

E. DATA MANAGEMENT AND ANALYSIS

Data Collection, Management and Storage. All participant data will be collected and stored on the password protected iPad, and all iPads will be maintained in accordance with Good Clinical Practices and FDA regulations, e.g. in locked cabinets in locked rooms with acess restricted only to study personnel. Once each month, data will be securely sent from LA Clinical Trials to the Arizona State University, where the data will be stored for analysis. We are currently implementing a different study together, and the data transfer has worked well.

Sample Size. The primary analysis of this study is to compare the quit rates between groups. The sample size estimation is based on the results from Oncken et al.⁶ the quit rates at 12 weeks for 0.5, 1.0 mg b.i.d. titrated groups and control group are approximately 45%, 60% and 15%. In an OTC setting, we assume the rates would reduce by half. Therefore, 23%, 30% and 8% are used to determine the sample size. Since we are interested in comparing the two active treatment arms with the control arm, to control for the overall type I error rate, the Bonferroni adjustment is applied: for each comparison, the type I error is 0.025. With 110 participants per group, we have at least 80% power to detect a difference of 23% vs. 8% (0.5mg vs. control) by the chi-square test. Even though a smaller sample size is required to detect a difference of 30% vs. 8% (1.0mg b.i.d. vs. control), we plan to enroll equal number of participants for each arm.

For the EMA component of the study, we anticipate the primary outcomes for each treatment condition in the EMA subgroup will not be statistically different from the non-EMA sample and plan to analyze the primary outcomes based on the combined sample. However, the data collected will provide information to quantify the longitudinal within subject association. In particular, we hypothesize that the severity of side effect will increase in the first 5 days after the initiation of treatment, and expect the odds of side effect at day 5 is three times the odds at day 1. Based on our simulations (type I error 0.05, 5 time points, and intra-class correlation 0.3), with 25 participants per group, we have at least 80% power to detect an odds ratio of 3.

Data Sharing Plan. The information that we will collect includes medically-related information that is protected and must remain confidential, so all standard methods to protect participant confidentiality will be employed, including maintaining information in password protected encrypted databases to reduce the risk of a data breach. Shared data across the two study sites will likewise be password protected and encrypted. After study completion, any outside requests for data will require a data sharing agreement that assures the following: (1) all data must be maintained in a secure fashion using appropriate technology, (2) commitment to use the data only for the research purposes requested, and (3) all shared data must either be destroyed or returned, including written assurances to that effect.

Statistical Analysis Plan

Main study. The participation flow will be reported following CONSORT guidelines. Intention to treat analysis will be applied for all statistical analyses. The data collected from the study will be summarized by the descriptive statistics for overall and by treatment condiction (1mg b.i.d., .5mg b.i.d. and placebo) and by the application of EMA (yes/no). The primary analysis will include estimating and comparing the guit rates between treatment arms. We will fit a logistic regression to model the probability of smoking cessation at 12 weeks with treatment condition, application of EMA and the interaction term of the two main effects as independent variables. If the interaction term is not significant, this implies the guit rates for the same treatment condition are similar in those with and without the utilization of EMA, and we will drop the interaction term and fit a model with main effects only. The comparison will be perfromed by the Wald test from the logistic regression with Bonferroni adjustment to account for multiple comparisons. The point estimate of guit rate and 95% confidence interval (CI) for each treatment condition will be reported. If the interaction term is significant, we will conduct the comparisons in EMA and non-EMA subgroups. A similar approach will be applied to the analysis of adherence and adverse events. These two outcome variables can be analyzed as a dichotomous (yes/no) or count variable (pill count and number of adverse events), and the logistic regression and Poisson regression will be used to evaluate whether group differences occur. In the secondary analysis, to evaluate

the impact of participant characteristics on the study outcomes, we will fit multivariable logistic or Poisson regression models. The odds ratio (from logistic regression) and ratio or percent change (from Poisson regression) will be reported to quantify the association.

In addition to evaluting the primary and secondary outcomes at the end of treatment (12 week), the trend over time between the initiation of treatment and at the end of the follow up period is also of interest. We will implement generalized linear mixed model (GLMM) with random intercept to account for the clustering effect (multiple visits clustered within each participant). Independent variables will include treatment condition, visit number, and other time-varying characteristics collected post radomization. We intend to use two-level GLMMs, and will perform exploratory analysis using 3-level GLMMs (visits clustered within participants, and participants clustered within sites [CA, AZ]), as we anticipate the variability from sites would be negligible.

Analysis of the Remote Cohort. We will assess the in-person and remote cohort data via separate analyses, but because the fundamental study design in the same for both, if the outcomes of the separate analyses suggest similar outcomes, we might combine the results of both groups into a single analysis.

EMA Statistical Analysis Plan. Our approach to analyzing EMA data is based on published approaches^{32,33} using GLMMs. This class of models is useful for analyzing EMA data because they allow multiple observations per subject, multiple levels of nesting (i.e., observations within weeks within subjects), multiple subject random effects, modeling of between-subjects (BS) and within-subjects (WS) variance as a function of time-invariant covariates (e.g. treatment assignment, gender, or nicotine dependence), and extension to non-normal outcomes (i.e., dichotomous, ordinal, counts). Our primary approach will be a three-level mixed model treating observations (level 1) within days (level 2) within subjects (level 3). Additionally, we will employ a time-varying effect model (TVEM)³⁴ if we find evidence that the relative association between momentary medication adherence, side effects, craving, and smoking varies over the two weeks of observation.³⁵ We present brief examples of analyses of central interest below.

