The two non-nicotine prescription medications, varenicline and bupropion, have not been considered for OTC status, in part because both had a 'box warning' placed on them by the FDA due to concerns that their use might cause or exacerbate psychiatric symptoms such as suicidal ideation or behavior. After multiple studies, including one of the largest smoking cessation trials ('EAGLES' study) ever conducted,¹⁷ it is clear that these medications do not cause statistically higher psychiatric adverse events than placebo or NRT. More specifically, in the EAGLES study, the FDA-approved dose of varenicline was found significantly more effective than bupropion, patch and placebo, and did not result in adverse events that necessitates a box warning, so the FDA removed the box warning. Thus, in combination with behavioral support, varenicline has the greatest probability of helping the most smokers quit with a similar adverse event profile to current OTC NRT products.

Given these data, the time has come to explore whether varenicline is safe and effective when no behavioral support is provided as a foundation to assessing whether it can be safe and effective as an over-the-counter medication. This is important because in real world use, smokers often do not receive behavioral support, so there is value in assessing whether varenicline quit rates will still be high without that behavioral support. Moreover, since the adverse events from varenicline have been shown to be comparable to the OTC nicotine patch, this research will assess whether varenicline, in two different doses, can be safe and effective without a healthcare provider prescription. More specifically, because earlier research found that .5mg twice a day (b.i.d.) varenicline is as effective as the currently FDA-approved 1.0mg b.i.d. dosing but with lower incidence of nausea and sleep disturbance⁶, there is value in assessing whether the lower dose will work as well as the higher dose in an OTC environment. Lastly, to understand the within-person mechanisms explaining *how* and *when* OTC varenicline might improve cessation outcomes, as well as how side effects affect medication adherence, we will also assess experience with OTC varenicline via ecological momentary assessment (EMA).

Primary Objectives

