- 1. To assess the safety and efficacy of the current FDA-approved 1 mg b.i.d. varenicline for smoking cessation in comparison with placebo when used in a simulated OTC study with no behavioral support provided.
- 2. To assess the safety and efficacy of .5mg b.i.d. varenicline in comparison with 1mg b.i.d. varenicline and placebo when used in a simulated OTC study with no behavioral support provided.

Secondary Objectives

- 1. To evaluate whether subject specific characteristics (e.g. socioeconomic status, ethnicity, smoking history, etc.) moderate primary (safety and efficacy) and secondary (adherence) outcomes.
- 2. To evaluate medication use patterns to assess whether varenicline is being used as indicated on the label, and to determine if medication adherence mediates cessation outcomes between-subjects.

3. In a subsample of participants, to examine how medication adherence, withdrawal, and side effects (e.g. nausea and sleep disturbance) vary within-subjects and are associated with smoking status using EMA in the first two critical weeks of medication use.

[figure not shown]
Hypotheses

- 1. Quit rates in the 1 mg b.i.d. varenicline condition will be significantly higher than the placebo medication condition when provided as an OTC medication.
- 2. Quit rates in the .5 mg b.i.d. varenicline condition will be comparable to the 1mg b.i.d. varenicline condition, and will be significantly higher than the placebo medication condition, when provided as an OTC medication.
- 3. Side effects will show a dose response relationship, with effects lowest in the placebo group.

C. EXPERIMENTAL METHODS Study Design

The primary objective of this study is to assess the efficacy of two different doses of varenicline used in a simulated OTC intervention relative to placebo (total N = 432). The design is a three-group placebo-controlled, double blind, block randomized clinical trial (as indicated in the figure), where participants will be randomly assigned to one of three

conditions: (1) 1 mg b.i.d. varenicline for 12 weeks, which is the current FDA-approved dose, (2) 0.5 mg b.i.d. varenicline for 12 weeks, or (3) placebo.

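### Hypothesis 2 predicts that 0.5 mg is comparable to 1 mg, but the SAP's only stated method for comparing arms is a difference test, with no interval for the dose difference

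*Combined protocol and SAP*

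**What the plan says.** **The question asked.** In B. Specific Aims, Primary Objective 2 is "To assess the safety and efficacy of .5mg b.i.d. varenicline in comparison with 1mg b.i.d. varenicline and placebo". Hypothesis 2 predicts the answer for the dose part: "Quit rates in the .5 mg b.i.d. varenicline condition will be comparable to the 1mg b.i.d. varenicline condition". It then adds superiority over placebo. The rationale in the same section says that "there is value in assessing whether the lower dose will work as well as the higher dose in an OTC environment".

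**The design.** Under C. Experimental Methods, Study Design, the main purpose is to "assess the efficacy of two different doses of varenicline used in a simulated OTC intervention relative to placebo", with 432 randomised in total. Sample Size (section E) halves the quit rates of an earlier trial for the OTC setting: "Therefore, 23%, 30% and 8% are used to determine the sample size" (0.5 mg, 1 mg and control respectively). It splits alpha over two tests only: "Since we are interested in comparing the two active treatment arms with the control arm", at 0.025 each.

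**The analysis.** The Statistical Analysis Plan, Main study, says: "The primary analysis will include estimating and comparing the guit rates between treatment arms". It continues: "The comparison will be perfromed by the Wald test from the logistic regression with Bonferroni adjustment to account for multiple comparisons". A point estimate and 95% CI of the quit rate are to be reported for each arm. The plan gives no interval for the 0.5 mg minus 1 mg difference, no margin, and no statement of what result would count as comparable.

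**The concern.** A prediction that two doses perform alike needs an analysis that can show how far apart they might be. A difference test can show only that they differ. When it fails to do so, the doses may be close or the trial may simply be too small to tell them apart. The plan's own sizing assumption puts 0.5 mg 7 points below 1 mg, so it matters which of these a null result would reflect.

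At stake is the dose-against-dose part of a primary objective. With no planned interval for the difference and no stated reading, whether the result is called comparable would be settled after the data are seen.

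**Working it through.** **Inputs**
- Quit rates: 1 mg 30%, 0.5 mg 23%, control 8% (Sample Size).
- Per-arm size: 110 in the power statement (Sample Size); 432 / 3 = 144 randomised (Study Design, 1:1:1 allocation).
- Alpha: 0.025 per placebo comparison (Sample Size). The plan states no alpha for a dose-against-dose test, so both 0.05 and 0.025 are shown.

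**Step 1. Reproduce the plan's own figure.** For 23% vs 8%, two-sided alpha 0.025, 80% power, chi-square test with pooled null variance and mean rate 0.155:

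n = [2.2414 × √(2 × 0.155 × 0.845) + 0.8416 × √(0.23 × 0.77 + 0.08 × 0.92)]² / 0.15²
= [2.2414 × 0.5118 + 0.8416 × 0.5007]² / 0.0225 = 2.4604 / 0.0225 = 109.4, so 110.

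Power is 80.3% at 110 per arm and 90.4% at 144. The stated sample size is correct for the placebo contrast.

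**Step 2. The same test applied to the doses.** For 30% vs 23% at 144 per arm:
- null SE = √(2 × 0.265 × 0.735 / 144) = 0.0520
- alternative SE = √((0.30 × 0.70 + 0.23 × 0.77) / 144) = 0.0518
- alpha 0.05: critical difference 1.96 × 0.0520 = 0.102; power ≈ Φ((0.07 − 0.102) / 0.0518) ≈ 27%
- alpha 0.025: critical difference 2.2414 × 0.0520 = 0.117; power ≈ Φ((0.07 − 0.117) / 0.0518) ≈ 18%

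Exact binomial enumeration of the logistic Wald test (no EMA term) agrees:

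| Per arm | True rates | Alpha | Power | Non-significant |
|---|---|---|---|---|
| 144 | 30% vs 23% | 0.05 | 26.6% | 73% |
| 144 | 30% vs 23% | 0.025 | 18.2% | 82% |
| 110 | 30% vs 23% | 0.05 | 21.5% | 78% |
| 110 | 30% vs 23% | 0.025 | 13.7% | 86% |

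If both doses are truly at 30% with 144 per arm, the test is non-significant 95% (alpha 0.05) or 98% (0.025) of the time. Non-significance is therefore the likely result in either case and separates them poorly.

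**Step 3. Overlap of the per-arm intervals.** At 144 per arm the two 95% CIs overlap 92% of the time at 30% vs 23%, and 99% of the time at equal 30%. Overlap is no better a guide.

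**Step 4. What the difference and its interval would give.** The half-width of the 95% CI for the difference is 1.96 × √(p₁(1 − p₁)/n + p₂(1 − p₂)/n):
- 144 per arm: 10.2 points at 30% vs 23%; 10.6 points at 30% vs 30%
- 110 per arm: 11.6 and 12.1 points

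If the observed rates equalled the sizing rates at 144 per arm, the interval would be −7 ± 10.2, or −17.2 to +3.2 points. A reader would see at once that a sizeable deficit had not been excluded. The estimate itself is also informative: an observed deficit of 7 points or more occurs 48% of the time at 30% vs 23% and 9% of the time at equal 30%.

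**Step 5. Is a formal comparability claim within reach?** The documents give no margin, so these are assumptions. For one-sided 0.025, 80% power and both doses truly at 30%, a non-inferiority margin of 10 points needs (1.96 + 0.8416)² × 2 × 0.30 × 0.70 / 0.10² = 330 per arm. A margin of 15 points needs 147. But 15 points is 15/22 = 68% of the 22-point advantage of 1 mg over control that the plan assumes (30% − 8%).

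**The case against.** The confirmatory design does not rest on this contrast. Study Design states the purpose relative to placebo, and Sample Size allots alpha only to the two placebo tests. The plan sizes the trial on unequal dose rates, so it does not itself assume equality. Within Hypothesis 2, only the placebo clause uses the language of significance, so the dose clause can fairly be read as descriptive. The per-arm estimates are promised, and an unadjusted difference with its interval can be computed from the counts. All of this stands, and it limits the weight of the point. It does not remove it: Primary Objective 2 names 1 mg as a comparator, and if the clause is descriptive the SAP should say so and report the difference.

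A reader might infer that the SAP intends to read a non-significant Wald test as showing comparability. The documents do not say that. The SAP does not name a 0.5 mg vs 1 mg test at all; it refers to comparisons between arms in general. The figures above show what would follow if that reading were adopted, not that the plan adopts it.

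A reader might also infer that the trial must become a non-inferiority or equivalence trial with a margin. That goes too far: reporting the dose contrast as estimation closes the gap without one.

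**Conclusion.** The point holds for the dose-against-dose part of Primary Objective 2 and Hypothesis 2. The one stated method for comparing arms cannot support the predicted answer. At the plan's own 30% vs 23% and 144 per arm it is non-significant 73% (alpha 0.05) to 82% (alpha 0.025) of the time, although 0.5 mg is truly 7 points worse.

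This rests on the plan's assumed quit rates, on all 432 participants being analysed together in three equal arms, and on a Wald test without the EMA term. The section on the remote cohort plans separate analyses first and makes pooling only a possibility. It gives no cohort sizes, so the loss of precision without pooling cannot be stated; the direction is wider intervals and lower power.

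It should not be read as a sample-size error. The 110 per group reproduces, and the placebo contrasts and their alpha are unaffected. Nothing here bears on which dose is appropriate. The point is worth fixing because the question is a stated primary one and the remedy is cheap.

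**What to change.** In the Statistical Analysis Plan, Main study:
1. Name the 0.5 mg minus 1 mg contrast, and pre-specify the intention-to-treat quit-rate difference with its two-sided 95% CI as its analysis.
2. State that neither a non-significant Wald test nor overlapping per-arm intervals will be read as comparability.
3. State the expected half-width: about 10 points at 144 per arm if the cohorts are pooled, wider if they are not.

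In Hypothesis 2, reword the dose clause as estimation of the difference. Keep comparable as a claim only if a justified margin is fixed before unblinding.

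**Cost.** A few sentences. Randomisation, data collection, sample size and the placebo tests do not change. The downside is that a comparability claim is probably out of reach at this sample size without a wide margin; stating this in advance is better than discovering it at reporting.
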